This clinical study is a non-randomized, single site, single-arm engineering clinical comparison study. The study is designed to collect and compare device parameters from the patient's current ventilator compared to the Helix ventilator.

V. Participant Enrollment

Following initial contact by their physician or his/her surrogate, participants/surrogate will be informed that their participation is entirely voluntary and the decision to participate or not, will in no way affect their further evaluation or therapy. Subsequently, the participant or surrogate will be given a complete and thorough explanation of the benefits and risks or discomforts that may be anticipated with this study. Informed consent will be obtained prior to enrollment in the study.

Sample Size:

Up to thirty (30) participants will be recruited for this study.

Engineering Evaluation of the Helix Family of Ventilators

Confidential

HRC-17067-HCPED-CC Version: 2.0, 26-Oct-2018

Page 15 of 21

VI. Study Procedures

Following the completion of the informed consent, participants enrolled in this study will be asked to use their existing ventilator for up to 1 hour to collect pressure and flow data for comparison purposes against the Helix ventilator.

Participants will then be set up on the Helix Ventilatory System using the same mode of therapy as their current ventilator. Participants may receive mechanical ventilation using any patient circuit currently being designed for the Helix Ventilator (Passive, Active with PAP, Active with Flow, or dual limb). Patients currently using non-invasive ventilation may be asked to use a mouth piece in lieu of a mask interface. While using the study device, therapy setting may be altered by the physician or his/her surrogate while maintaining the ventilator needs of the patient. For e.g., a patient currently prescribed an SIMV mode may temporarily be switched to a pressure control mode to assess patient synchrony and ventilator performance.

Once the participant is set-up, he/she will be asked to use the ventilator for up to 4 hours. During this time, Philips Respiration engineers will be collecting data through several mechanisms: 1) Helix SD Card, 2) NICO Monitoring System, and / or 3) External data collection device (ex. laptop). The study staff may ask the participant's opinions on the comfort of the therapy delivery. There will be no invasive monitoring as part of this study.

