The engineering evaluations will take place at the Boston Children's Health Physician offices. The study investigators, respiratory therapist, and/or other qualified clinical staff, will be supervising and present for all study visits. Philips Respiration engineers will be present for observational purposes only. All study staff working on this trial will be trained to the protocol and device prior to beginning work.

Participants may be asked to participate in this data collection study up to six (6) times.

Study data collected for this study will be collected on paper or electronic source records. These records will include information regarding inclusion/exclusion, performed study procedures and questions regarding device use. Only those staff that have been delegated by the Principal Investigator will be able to enter or make changes to the data in the Case Report Forms.

Engineering Evaluation of the Helix Family of Ventilators

Confidential

HRC-17067-HCPED-CC Version: 2.0, 26-Oct-2018

Page 16 of 21

VII. Statistical Analysis

The purpose of this Engineering study is to collect engineering and subjective data on the Helix Ventilatory System and the patient's existing ventilator device for comparison purposes. Therefore, no formal analysis of the data is planned.

Determination of Sample Size

Up to 30 participants will be enrolled in the study. Since this is an engineering study to address issues which arise, no sample-size calculation was performed.

General Considerations

The primary analysis will be performed including all completed participants. Descriptive data tables will be provided for all variables of interest. Continuous data will be presented by mean, standard deviation, median, minimum, and maximum observation. Data will be presented in the untransformed and transformed format (if applicable) for each continuous variable. Categorical data will be presented as frequencies and percentages. All analyses will be conducted using either SAS® or SPSS® software.

Participant Disposition

Participant disposition, including the total number of participant's enrolled, completed, early terminations and withdrawals, will be presented overall and by software version. A listing will be provided with the reasons for discontinuation.

Demographics and Baseline Characteristics

Standard subject demographics (e.g., age and gender) and baseline characteristics will be summarized for all participants enrolled and for evaluable participants.

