The privacy of each subject and confidentiality of his/her information shall be preserved in reports and when publishing any data. Except when required by law, participants will not be identified by name, social security number, address, telephone number, or any other direct personal identifier in study records. For records disclosed outside the Philips Respiration, participants will be assigned a unique code number.

Results of the study related data, medical history, and information obtained from the questionnaires and device data will be reported and received by Philips Respiration. Philips Respiration will use participant study data for research purposes to support scientific and marketing objectives described in this protocol.

In addition, participant records may be reviewed in order to meet federal and state regulations. Reviewers may include representatives from the FDA or similar government authorities in other countries where the device is being used, and Philips Respiration for the purposes of the following side effects, and to gather additional information related to the study, and the Institutional Review Board (IRB). Participant permission for review of confidential information is granted by signing the associated informed consent. Philips Respiration will ensure that it follows all applicable state and federal data protection regulations.

Withdrawal Criteria:

The term “discontinuation” refers to the participant’s premature withdrawal from the study prior to completing all procedures. Participants may be discontinued from the study for any of the following reasons:

Engineering Evaluation of the Helix Family of Ventilators

Confidential

HRC-17067-HCPED-CC Version: 2.0, 26-Oct-2018

Page 19 of 21

- If in the investigator's judgement, continuation in the study may prove harmful to the participant. Such a decision may be precipitated by adverse events, including fever, nausea, rash, changes in vital signs, or the development of a new medical condition. The investigator will be solely responsible for making medical/safety decisions regarding the participant's continued participation in the study.
- Noncompliance;
- At the request of the participant.

The study team will document whether or not each participant completed the study. If, for any participant, study treatment or assessments were discontinued, the reason will be recorded.

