The study goal is to have 30 participants to complete throughout the study. If a subject withdraws from the study, they will not be replaced. All data collected from participants will be used in the data analysis unless the participant has stated they do not want their data to be used.

Hard copies of the study will be kept on site for at 2 years after study completion. The sponsor will maintain study records indefinitely.

IX. Potential Benefits

Although participation in this trial will not result in any direct benefit to the participant, they will be contributing to generalizable data that will help improve device design and function. The advancements with the Helix platform may ultimately improve patient outcomes by allowing the ventilator to provide better ventilation for the patient.

X. Monitoring and Quality Assurance

All adverse events, serious and non-serious, occurring during the course of the study will be collected, fully documented, and reported to the Institutional Internal Review Board by the Principal Investigator or study staff. Serious adverse events will be reviewed by the Sponsor within 24 hours of the study team being aware of the event. For each adverse event, the investigator will provide the onset, duration, intensity and treatment required, outcome and action taken. We anticipate that adverse events during this study would be minimum. Participants will only be using the therapy for 4 hours under the supervision of clinicians. All reasonable care will be taken to avoid these complications. In addition to adverse event reporting, the investigators will report a summary of the protocol findings, participant recruitment, drop-outs, and events to the IRB annually.

Engineering Evaluation of the Helix Family of Ventilators

Confidential

HRC-17067-HCPED-CC Version: 2.0, 26-Oct-2018

Page 20 of 21

All device deficiencies, use or user errors, and equipment failures will be documented. Use or User errors will be captured as part of the source documentation. Device deficiencies and equipment failures will be kept on a separate log. The serial numbers and type of deficiency/failure will be captured.

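### Two inclusion rules, completers only and all collected data, are left unreconciled for the primary tables, and the evaluable set has no criterion

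*Combined protocol and SAP*

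**What the plan says.** Section VII, General Considerations, sets the population for the main analysis: "The primary analysis will be performed including all completed participants". The same paragraph plans descriptive tables with mean, standard deviation, median, minimum and maximum.

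The Withdrawal Criteria (section VIII) give a broader rule, placed directly after the statement that withdrawn participants are not replaced: "All data collected from participants will be used in the data analysis unless the participant has stated" an objection to that use.

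The Withdrawal Criteria also come closest to defining completion. Discontinuation is "premature withdrawal from the study prior to completing all procedures". Harm, in the investigator's judgement, is one listed reason, and "Such a decision may be precipitated by adverse events". On records, "The study team will document whether or not each participant completed the study", and where "study treatment or assessments were discontinued, the reason will be recorded".

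Section VII, Demographics and Baseline Characteristics, calls for summaries of all enrolled participants and of *evaluable* participants. No criterion for *evaluable* is given there, and the alphabetical glossary has no entry where the term would fall.

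**The concern.** The study exists to verify how Helix performs. Participants whose Helix use ended badly are among the most informative about that, and a completers-only rule is the rule most likely to leave them out. If someone is discontinued because of an adverse event, or after a device problem, the waveforms recorded up to that moment would be absent from the primary tables. The reported minimum and maximum are each a single observation, so one omitted participant can change them.

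There is also a problem of reproducibility. One analyst following section VII and another following the Withdrawal Criteria would build different primary datasets, and each could point to the plan in support. The undefined *evaluable* set adds a further population that neither could construct from the text.

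**Working it through.** There is no plan figure to reproduce: section VII states that no sample-size calculation was performed, and the documents give no standard deviation, effect or numerical drop-out rate. The check is mainly a comparison of the text.

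**1. Do the two rules select the same people?** Section VII selects completed participants. The Withdrawal Criteria select everyone with collected data, less refusals. They differ for any participant who was discontinued, had data recorded beforehand and did not refuse its use.

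**2. Does any text assign the rules to different analyses?** Section VII speaks of the primary analysis and the Withdrawal Criteria of the data analysis in general. Completers could feed the primary tables and all data could feed others, but no section says so or names such a second performance analysis.

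**3. What does *completed* mean?** Since discontinuation is leaving before all procedures are finished, a completer is by implication a participant not discontinued. Under section VI (Study Procedures), participants are "asked to use their existing ventilator for up to 1 hour to collect pressure and flow data", and once set up on Helix "he/she will be asked to use the ventilator for up to 4 hours". These are ceilings, so a shorter session is not in itself a missed procedure. Repeat sessions, up to six, are optional.

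**4. Can the excluded group be related to device performance?** Yes, by two routes.
- An adverse event may lead to discontinuation (Withdrawal Criteria).
- If a problem is identified, the respiratory therapist removes Helix and returns the participant to their own device (section VIII). The text does not equate this with leaving the study, so this route operates only if discontinuation follows.

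**5. What can be said about size?** Inputs: enrolment of at most 30 (section VII, Determination of Sample Size) and no replacement (Withdrawal Criteria).
- Headcount share of one excluded participant at the cap: 1/30 = 3.3%. It is larger if fewer are enrolled.
- Illustration only. Let k of 30 participants be excluded and let their mean differ from the completers' mean by δ standard deviations. The all-data mean then differs from the completers' mean by kδ/30. With δ = 1 (an assumption):

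| k excluded | Shift in mean (SD) |
|---|---|
| 1 | 1/30 = 0.03 |
| 3 | 3/30 = 0.10 |
| 6 | 6/30 = 0.20 |

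With δ = 0, or with nobody excluded, the shift is zero. The documents supply neither k nor δ.

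**The case against.** The best defence is that little is at stake. Section VII plans no formal analysis, there is no decision rule, and drop-out is expected to be low. Discontinuations appear in the disposition table and a listing of reasons, adverse events are listed, and device deficiencies go on a separate log. Removal of Helix at one visit need not end participation, because further sessions are allowed. A participant who leaves before Helix set-up has no Helix data under either rule. All of this stands and keeps the point minor. It does not settle which dataset to build, and the listings and log are not said to return the omitted pressure, flow or volume values to the performance tables.

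Three stronger readings are tempting, and the documents do not support them.
- *That the two rules cannot both hold.* They can, if each governs a different analysis. The plan simply does not say so.
- *That completion has no usable meaning.* The Withdrawal Criteria give one by implication, and staff must record completion status. Nor does the mention in Trends Analysis of participants who try only one iteration make completion unclear: the comparisons there are between device hardware and software versions, so an iteration is a version, not a session.
- *That the primary tables will be biased in favour of Helix.* This needs a discontinuation linked to performance, usable recordings before it, and exclusion of those recordings. It is possible, not shown.

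**Conclusion.** The point holds as a minor one. The plan states a completers-only rule for the primary analysis and an all-data rule for the data analysis, does not say which governs the primary tables, and names an evaluable set without a criterion. Under the completers rule, recordings from a participant discontinued for an adverse event, or after a device problem, would be left out of the primary performance tables, with a possible tilt towards Helix. The size cannot be computed and may be zero; the shifts shown rest on assumed numbers of exclusions and an assumed difference of 1 SD. The conclusion rests on reading a completer as a participant not discontinued, which the Withdrawal Criteria imply but do not state.

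**What to change.** Replace the completers sentence in General Considerations with:

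> The primary analysis includes all data collected from all enrolled participants, including data recorded before any early removal of Helix or withdrawal, except data from participants who refuse its use (as in the Withdrawal Criteria). Helix summaries use all participants with any Helix recording; comparisons with the existing ventilator use all participants with recordings on both devices. Early removals are reported with their reason, out of all participants set up on Helix.

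Then:
- Label any completers-only summary as supportive, with *completed* defined as not discontinued under the Withdrawal Criteria.
- In Demographics and Baseline Characteristics, replace *evaluable participants* with *participants with recordings on both devices*.
- List recording duration beside the summaries, so that an extreme value from a very short recording can be recognised.

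The cost is a few sentences and one listing. The change applies the sponsor's own rule, and the reason for stopping treatment or assessments is already to be recorded. The downside is that some short recordings enter the summaries, and the figures may look slightly less favourable. How several sessions from one participant enter the tables is a separate question that this change does not settle.

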Therapy Modes for Helix Ventilator

The device that is being evaluated in this study can provide many different modes of therapy in both pressure support and volume controlled ventilation.

The following is a list of modes that may be provided with these devices, dependent on patient prescriptions:

- Continuous Positive Airway Pressure (CPAP) with optional C-Flex
- Spontaneous Pressure Support (S) with optional Bi-Flex
- Spontaneous/Timed Pressure Support (S/T)
- Pressure Control Pressure Support (PC)
- Timed Pressure Support (T)
- Averaged Volume Assured Pressure Support (AVAPS) in conjunction with the modes listed above (S, S/T, PC, T)
- Volume Control Ventilation (CV)
- Volume Assist Control (AC)
- Synchronous Intermittent Mandatory Ventilation (SIMV)
- Pressure Control SIMV (PC SIMV)
- Pressure Regulated Volume Control (PRVC)

Target Patient Population

The patient population is extremely varied. The patient's age will vary from infant ($\geq 5\text{kg}$) to adult. The medical condition of the patient population ranges from critically ill acute respiratory conditions to pre-existing or developing chronic conditions. Patients treated with the Helix ventilator may suffer from diseases or injuries requiring invasive or non-invasive ventilation. Many of these diseases result in respiratory failure, which can be classified as acute or chronic. Acute respiratory failure is typically treated in a hospital ICU or sub-acute hospital, while chronic respiratory failure is treated at home or in a long term care facility. Specific examples of respiratory failure include, but are not limited to:

- Neuromuscular diseases leading to respiratory failure: Amyotrophic Lateral Sclerosis (ALS), Spinal Muscular Atrophy (SMA), Duchenne Muscular Dystrophy (DMD)

Engineering Evaluation of the Helix Family of Ventilators

Confidential

HRC-17067-HCPED-CC Version: 2.0, 26-Oct-2018

Page 13 of 21

- Chronic Obstructive Pulmonary Disease (COPD)
- Asthma
- Spinal cord injuries
- Thoracic cage deformities
- Pneumonia originating from infectious disease such as influenza
- Pulmonary edema (symptom of congestive heart failure)
- Trauma leading to Acute Lung Injury (ALI)
- Acute Respiratory Distress Syndrome (ARDS)

II. Study Objective

The objective of this Engineering study is to verify the overall performance and controls of the Helix Ventilator.

Specific Aims

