1. To collect and compare pressure and flow data between the participant's current therapy device and the Helix ventilator in either invasive or non-invasive ventilation. Pressure and flow waveform data will be evaluated to assess ventilator performance such as delivered pressure such as volume control accuracy, patient synchrony (triggering/cycling), and measured/calculated parameter accuracy.
2. To evaluate the therapy delivery using alternate circuit types, such as mouthpiece ventilation (MPV) or passive dual limb
3. To obtain participant feedback regarding the comfort of the therapy delivery.
4. To obtain caregiver feedback related to the usability of the study device
5. To evaluate the alarm functionality of the study device.
6. To compare the device's Spirometry measurement while it is operating on standard and alternative circuits, (Tidal Volume, breath rate, Peak flows) against a control measurement device

III. Subject Selection

Participants will be recruited from Boston Children's Health Physician's Group. Initial contact will be made by the participant's physician, or by his/her designee

Engineering Evaluation of the Helix Family of Ventilators

Confidential

HRC-17067-HCPED-CC Version: 2.0, 26-Oct-2018

Page 14 of 21

Inclusion Criteria

Participants who are currently using mechanical ventilation (> 1 month at time of study participation) as part of medical care and have demonstrated a clinically acceptable response to this therapy and meet the following inclusion criteria:

1. Weight \geq 5Kg;
2. Any medical condition requiring mechanical ventilation through nasal/facial mask, mouthpiece or tracheostomy
3. Any medical condition requiring mechanical ventilation for > 1 month

Exclusion Criteria

1. Participants intubated with an endotracheal tube
2. Clinically unstable, i.e.,
 - a. Acute Respiratory Failure
 - b. Participants with refractory hypotension (defined as systolic blood pressure less than 90 mm Hg despite inotropic agents)
 - c. Uncontrolled cardiac ischemia or arrhythmias
 - d. Any participant determined as inappropriate for the study by the Principal Investigator
3. Patients suffering from metastatic or terminal cancer
4. Currently employed by a manufacturer of respiratory products or family member employed by a manufacturer of respiratory products
Patient of surrogate is unable to provide informed consent

IV. Study Design

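### Could the current-ventilator and Helix columns be weighted differently because the plan never defines one record per person?

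*Combined protocol and SAP*

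**What the plan says.** Specific Aim 1 (section II) is "To collect and compare pressure and flow data between the" participant's own device and Helix, and section IV describes the study as that comparison. Section VI gives the sequence. After consent, participants are "asked to use their existing ventilator for up to 1 hour to collect pressure and flow data for comparison purposes" with Helix. Then "Participants will then be set up on the Helix Ventilatory System using the same mode of therapy as their current ventilator", and they are "asked to use the ventilator for up to 4 hours". On the study device there is latitude: "While using the study device, therapy setting may be altered by the physician or his/her surrogate", any of four circuit types may be used, and a mouthpiece may replace a mask. The same section adds: "Participants may be asked to participate in this data collection study up to six (6) times".

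Section VII says that no formal analysis is planned and that no sample-size calculation was done for the cap of 30. The primary analysis covers completed participants. The continuous summary is "Continuous data will be presented by mean, standard deviation, median, minimum, and maximum observation". Trends Analysis lists paired and repeated-measures tests between device versions, to be used only if formal testing is required. Nothing in sections VI or VII names the summary unit, says which Helix segment supplies a person's value, or says whether the recording on the current ventilator is made again at a later participation.

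**The concern.** The descriptive tables are the only output the plan firmly commits to, so an undefined unit affects the main product of the study. The two devices are not recorded symmetrically. At the stated limits one person can give 6 × 4 = 24 hours on Helix, against 1 hour on the current ventilator if it is recorded once, or 6 × 1 = 6 hours if it is recorded each time. Thirty people can give between 30 and 30 × 6 = 180 Helix visit records.

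If the current-ventilator column had one value per person and the Helix column one per visit, frequent attenders would weigh more in the second column than in the first. The protocol says of its target population that "The patient population is extremely varied", from 5 kg infants to adults. Where an endpoint differs widely between people, unequal weighting could therefore look like a device difference. Pooling Helix recordings made after a change of settings would also mix the effect of the setting with that of the device. Two analysts could build different tables from the same data.

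**Working it through.** The plan gives no figure to reproduce, so the check asks when the weighting artefact can arise and how large it would be.

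**Inputs from the documents:** up to 30 participants (sections V and VII), and 1 to 6 participations each (section VI). **Assumed, because the documents are silent:** how attendance is spread, and how attendance relates to the endpoint.

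**Model.** The devices are identical and person *i* has a constant value x_i and n_i visits. The gap between column means is Σ(a_i − b_i)x_i, where a_i and b_i are the weights in the Helix and current-ventilator columns.

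| Current ventilator recorded | Table unit | Helix weight | Current weight | Gap |
|---|---|---|---|---|
| every participation | visit | n_i/Σn | n_i/Σn | 0 |
| every participation | person | 1/30 | 1/30 | 0 |
| once | person | 1/30 | 1/30 | 0 |
| once | visit | n_i/Σn | 1/30 | not 0 unless attendance is equal or happens to balance |

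Only the last row produces an artefact.

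**Size in that row.** In between-person SD units, the chance SD of the gap is √Σ(n_i/Σn − 1/30)².

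- 5 people attend six times and 25 once: Σn = 55, and the frequent attenders supply 30/55 = 55% of records. √[5(6/55 − 1/30)² + 25(1/55 − 1/30)²] = √(0.0287 + 0.0057) = 0.186.
- 10 and 20: Σn = 80, share 60/80 = 75%. √(0.0174 + 0.0087) = 0.161.
- 20 and 10: Σn = 130, share 120/130 = 92%. √(0.0033 + 0.0066) = 0.099.
- Five people at each of 1 to 6 visits: Σn = 105, Σn² = 455. √(455/105² − 1/30) = 0.089.
- Equal attendance: 0.

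If attendance correlates *r* with the endpoint, the systematic gap is r × CV(n). The CV is 1.016, 0.884 and 0.544 in the first three patterns. That gives 0.203, 0.177 and 0.109 SD at r = 0.2, and 0.508, 0.442 and 0.272 SD at r = 0.5. These gaps too become zero in the first three rows of the table.

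**A concrete case (assumed values).** Twenty-four people attend once with 400 mL on both devices, and six attend six times with 100 mL on both.

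- Current ventilator once per person: (24 × 400 + 6 × 100)/30 = 340 mL.
- Helix per visit: (24 × 400 + 36 × 100)/60 = 220 mL, a false gap of −120 mL.
- Current ventilator recorded at every visit: also 220 mL, so the gap is 0.
- Per person: 340 against 340, so the gap is 0.

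**A yardstick.** With one record per person per device, and correlation ρ between recordings of the same person, the chance SD of the mean within-person difference is √[2(1 − ρ)/(30ρ)] between-person SD. That is √(1.4/9) = 0.39 for ρ = 0.3, √(1/15) = 0.26 for ρ = 0.5, and √(0.4/24) = 0.13 for ρ = 0.8, all assumed values. Even in the unfavourable row, the chance artefact is of the same order as, or smaller than, the noise that 30 people leave in the best available contrast.

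**Which row do the documents point to?** Section VI describes a single sequence, own ventilator and then Helix, and says that people may take part in the data collection up to six times. Taking part again most naturally means repeating the sequence. The reference to completing consent leaves the other reading open. On the unit, section VII defines its primary set by completed participants, and the Trends Analysis tests are within-subject or between-subject. Paired t, Wilcoxon, RMANOVA, Friedman and Cochran's Q all take one value per person per condition. The plan's habit is therefore to count people.

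**Altered settings and circuits.** Aim 2 treats alternate circuits as a question of its own, and aim 6 separates standard from alternative circuits. Helix starts in the participant's existing mode, so a like-for-like segment will usually exist. An analyst following the aims would tabulate changed conditions in their own rows.

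**The case for a change.** The strongest reply is that a natural reading is not a written rule. Section VIII, under Withdrawal Criteria, says that all collected data will be used. Taken literally, that brings every visit and every altered segment into the tables. The lack of formal testing is no defence either, because a misleading descriptive mean is still misleading. Even if the own-ventilator recording is repeated, changes of settings are described only for Helix, so pooled Helix data would still mix setting and device.

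Part of this stands. The unit, the choice of segment and the repetition of the own-ventilator recording are indeed unwritten, and in the one unfavourable row of the table the artefact is real. The all-data sentence carries less weight than it seems to. It follows a statement about not replacing withdrawals, and it concerns whose data are kept, not how recordings are reduced to a table entry. Using all data is compatible with one summary per person and separate rows by condition. The confounding of settings needs an analyst to pool conditions that the aims list separately. The tidal-volume example also overstates relevance. Aim 1 names delivered pressure, volume control accuracy, synchrony and parameter accuracy, none of which is shown to scale with body size. Tidal volume appears in aim 6, where the comparator is a control measurement device and not the participant's own ventilator.

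**Conclusion.** The gap in wording is real, but it does not call for a change to the plan. A weighting artefact needs three things together: own ventilator recorded once, Helix tabulated by visit, and unequal attendance. Its chance SD is then 0.09 to 0.19 between-person SD under the assumed patterns. It is larger, 0.11 to 0.51, only if attendance is also assumed to correlate 0.2 to 0.5 with the endpoint. It is zero if the sequence is repeated at each participation with both devices tabulated on the same unit, or if values are summarised per person. The settings problem needs the further step of pooling conditions that the aims keep apart.

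No stated rule or figure is shown to give a wrong result. The study is an engineering evaluation with descriptive output, no planned formal analysis and no stated success criterion, so no decision in the documents turns on these means. Naming the unit and labelling the rows is ordinary work in preparing table layouts. This conclusion rests on reading repeat participation as repeating the sequence, or on the analyst counting people, as section VII does elsewhere. Attendance and correlations are assumptions throughout.
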